7. RISKS

- 7.1 Breach of Confidentiality – There is an unlikely potential risk of a breach of confidentiality.
- 7.2 Radiation – Study participants will be exposed to radiation from the mammography imaging. There is an extremely low risk that the radiation may cause cancer or other radiation effects years after the study. Exposure to the radiation through this study is a part of routine healthcare.
- 7.3 Risk of an Unexpected Imaging Finding – There is a risk that an unexpected imaging finding could be detected. In many cases, these are of benefit to the patient, such as detection of a unexpected cancer. In some cases, the unexpected finding may be indeterminate, such as a renal mass that is not clearly benign or malignant. Indeterminate findings may need additional workup that will not be covered as a part of this study.

8. PRECAUTIONS / MINIMIZATION OF RISKS

Participants will be monitored by study personnel for risks—physical, psychological, social, economic, and/or legal—that participants may encounter during their participation in this study or as a result of DECT imaging and data collection required in this protocol.

- 8.1 Breach of Confidentiality – The research team is experienced and will utilize best practices to avoid a breach of confidentiality. The risk of confidentiality will be minimized by collecting only the data that is required by the study, labeling all data forms and samples with a coded identifier, and maintaining all study records in locked files or password-protected computer files.
- 8.2 Radiation – The radiation used in this study is a part of the patient's standard of care. No additional radiation is being used due to the study.
- 8.3 Risk of an Unexpected Imaging Finding – All of the research DECT liver CTs will be interpreted by a radiologist, a physician with expertise in CT imaging. A formal report will be placed permanently in the electronic medical records. Clinically significant unexpected imaging findings will be communicated by phone with the gastroenterologist, per standard of care at UAB.

9. BENEFITS

If our hypothesis is true that retracting the clip 5 mm before clip deployment will help to decrease clip migration, this will help improved accuracy of biopsy site localization and in cases of malignancy, will allow for less complicated, better localized, and improved results of tumor targeting for surgical resection. If the hypothesis does not hold true, than this method of clip deployment should no longer be used as it does nothing to improve clip migration.

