3. OBJECTIVES

3.1 Primary Objective

To determine which method decreases clip migration better, retracting the clip deployment apparatus 5 mm before deployment or not retracting.

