3.2 Secondary Objectives

- 3.2.1** Compare different breast densities (entirely fatty, scattered fibroglandular densities, heterogeneously dense, extremely dense) and their impact on clip migration in both groups (retracted vs nonretracted).
- 3.2.2** Compare different approaches (lateral, medial, superior) to biopsy and evaluate if they have an impact on clip migration in both groups (retracted vs nonretracted).
- 3.2.3** Evaluate if thinner or thicker breasts result in more or less clip migration in both groups (retracted vs nonretracted).
- 3.2.4** Evaluate if patient's age correlates with more or less clip migration in both groups (retracted vs nonretracted).

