12.1 Sample size justification

A total of 250 female patients presenting to UAB for stereotactic biopsy will be randomly assigned as 1:1 ratio to Arm1 (n=125) with advancing the clip to the biopsy site and deploying, or Arm2 (n=125) with advancing the clip to the biopsy site and retracting 5 mm and then deploying. Our hypothesis is that retracting to clip 5 mm before clip deployment will decrease clip migration, e.g. only 20% or less of breast biopsy patients who will have significant migration (greater than 10 mm from the biopsy site) while advancing the clip to the biopsy site and deploying without retracting will have at least of 50% significant migration. This size of 125 in each arm will have 99.9% power to test 30% difference (20% vs 50%) or >90% power to test at least 20% difference in proportion of patients who will have significant migration using one-sided Fisher's Exact test at 5% significant level (Table 1).

Table 1 Statistical Power to Test Differences Between Two arms.

Significant migration in Arm1 (%)	Significant migration in Arm2 (%)	Type I error (%)	Power (%)
50	15	5	100
50	20	5	99.9
50	25	5	99.1
50	30	5	93.1
50	15	1	100
50	20	1	99.6
50	25	1	95.4
50	30	1	78.5

A sample size of 125 will also produce two-sided 95% confidence interval to estimate the mean distance of migration with 0.177 standard deviation to the limits for each arm. Patients enrollment is expected to be completed within one year.

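### Section 9 says retraction has no effect on clip migration if the hypothesis fails, but the planned tests and intervals cannot support that conclusion from a non-significant result

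*Combined protocol and SAP*

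**What the plan says.** The primary objective (section 3.1) is a comparison of two techniques: "To determine which method decreases clip migration better, retracting the clip deployment apparatus 5 mm before deployment or not retracting". Section 9 frames the hypothesis as directional ("If our hypothesis is true that retracting the clip 5 mm before clip deployment will help to decrease clip migration") and then says what follows for migration if it fails: "If the hypothesis does not hold true, than this method of clip deployment should no longer be used as it does nothing to improve clip" (last word cut). No other section qualifies that statement.

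Section 12.1 describes the allocation ("will be randomly assigned as 1:1 ratio to Arm1 (n=125", with the same number in Arm 2) and the design test ("using one-sided Fisher's Exact test at 5% significant level (Table 1"). It assumes significant migration in at least 50% without retraction and at most 20% with it, and also claims ">90% power to test at least 20% difference in proportion of patients who will have significant migration using one-sided Fisher's Exact test".

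Section 13.2 plans a Clopper-Pearson 95% interval for the proportion in each arm, a Fisher test between arms (sidedness not stated), a normal-approximation 95% interval for the mean distance in each arm, and a two-group t-test on distance. It plans no interval for the between-arm difference on either scale. The logistic regression is listed under the secondary objectives. It reports odds ratios with intervals only for factors that contribute significantly, so it would not supply an interval for a non-significant arm effect.

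**The concern.** A superiority test that is not significant shows that a reduction was not demonstrated. To say that a technique has no effect, one needs an interval for the between-arm difference that is narrow enough to exclude the reductions of interest. The plan has neither that interval nor a margin to read it against.

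What is at stake is how a null result is reported. Section 9 is the only text in the documents on a failed hypothesis, and it attaches a consequence for practice to it. A report that follows it could describe an inconclusive result as evidence of no effect.

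**Working it through.** **Inputs.** From section 12.1: n = 125 per arm, one-sided Fisher's exact test at 5%, 50% significant migration in Arm 1, differences of 20 and 30 points. True rates of 40% and 35% in Arm 2 are illustrations; the documents do not give them.

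**Step 1: reproduce Table 1.** Power is the sum, over all pairs (x1, x2) from 0 to 125 with one-sided hypergeometric p ≤ 0.05, of Bin(x1; 125, p1) × Bin(x2; 125, p2).

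| Arm 1 v Arm 2 | Table 1 | Recomputed |
|---|---|---|
| 50% v 20% | 99.9% | 99.96% |
| 50% v 25% | 99.1% | 99.2% |
| 50% v 30% | 93.1% | 93.5% |

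The plan's figures reproduce, so the sample size is not at fault.

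**Step 2: extend the same calculation below the tabulated differences.**

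| Arm 1 v Arm 2 | Power | Non-significant |
|---|---|---|
| 50% v 35% | 75.2% | 24.8% |
| 50% v 40% | 45.0% | 55.0% |

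If the Fisher test in section 13.2 were run two-sided, power at 50% v 40% would be 30.6%, so the test would be non-significant 1 − 0.306 = 69.4% of the time.

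**Step 3: what a null leaves open, for proportions.** The Newcombe interval for the reduction d = p1 − p2 uses the Wilson limits (l, u) of each arm:

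- lower = d − √[(p1 − l1)² + (u2 − p2)²]
- upper = d + √[(u1 − p1)² + (p2 − l2)²]

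*Equal counts, 62/125 in each arm (49.6%).* The Wilson limits are 0.4098 and 0.5825. The half-width is √(0.0862² + 0.0865²) = 0.122, so the interval is −12.2 to 12.2 points. The simple normal formula agrees: 1.96 × √(2 × 0.5 × 0.5 / 125) = 0.124.

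*A just non-significant result, 62/125 v 49/125 (49.6% v 39.2%).* One-sided Fisher p = 0.063 and d = 10.4 points. The Wilson limits for 49/125 are 0.3109 and 0.4796.

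- Upper: 0.104 + √(0.0865² + 0.0811²) = 0.223
- Lower: 0.104 − √(0.0862² + 0.0876²) = −0.019

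The interval runs from −1.9 to 22.3 points, so it still contains the protocol's own 20-point difference.

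**Step 4: the same question for distance.** Section 12.1 gives a per-arm half-width of 0.177 standard deviations (SD), which reproduces as t(0.975; 124)/√125 = 0.177. With equal SDs, the half-width for the difference in means is about 0.177 × √2 = 0.25 SD. Equal observed means would therefore leave reductions of up to about a quarter of an SD open. The documents give no SD in millimetres.

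**The case against.** **Status of the sentence.** It stands in the Benefits section, not the analysis plan, and it speaks of the hypothesis being untrue, not of a p-value. Sections 12.1 and 13.2 contain no rule equating non-significance with no effect. A reader might infer that the protocol sets a formal decision rule; the documents do not support that. What survives is that the hypothesis will in practice be judged by superiority-type tests, and that no planned output could establish the statement.

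**A null would be informative.** From a 50% control rate, a true 20-point difference would be missed only 6.5% of the time, and a 30-point difference almost never. This stands. It supports saying that a large reduction is unlikely, not that there is none.

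**The t-test is left out of the miss rates.** This also stands. The t-test on distance has 80% power at about 0.32 SD one-sided or 0.36 SD two-sided with 125 per arm. The 55% is therefore the miss rate of the Fisher test, not the chance that the whole trial shows no decrease. But the t-test is also a superiority test, and its non-significance has the same limit.

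**Worthwhile reductions.** A reader might infer that reductions worth having would be missed. The documents name no smallest worthwhile difference, so the 10-point case is only an illustration.

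**Subgroups.** A reader might also infer from the secondary objectives in section 3.2 that an overall null could hide benefit in some women and harm in others. Nothing in the documents gives evidence of this, and those analyses go ahead whatever section 9 says. The point does not rest on it.

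**Conclusion.** The point holds as a fault of inference and reporting. It does not touch the sample size, the significance level, the endpoint or the primary test. A non-significant result here would count against reductions of 20 to 30 points from a 50% control rate. It would not show absence of effect: the Fisher test misses a true 50% v 40% in 55% of trials, and even identical observed rates near 50% leave up to about 12 points open.

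These figures assume 125 analysed patients per arm, the one-sided 5% test, and the 50% control rate of section 12.1. They describe the endpoint of migration over 10 mm only. Whether retraction should stay in use is a clinical decision on which this review takes no position; the point is only that the reason section 9 gives would not follow from a null result.

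**What to change.** 1. In section 9, replace the inference of no effect with wording such as: *A non-significant result will be reported as not having demonstrated a reduction in clip migration.*
2. In section 13.2, add a two-sided 95% confidence interval for the between-arm difference in the proportion with migration over 10 mm (for example Newcombe), and one for the difference in mean distance. Require the report to state which reductions each interval does and does not exclude.
3. If a margin is used, fix and justify it before data review, and say only that a reduction of that size or larger has been excluded. A margin as wide as 20 points must not be turned into absence of benefit. For example, 62/125 v 52/125 (an observed 8-point reduction, one-sided p = 0.127) has a Newcombe interval of −4.3 to 19.96 points. It would pass such a margin while leaving almost 20 points open.

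The cost is a few sentences of protocol and SAP wording, with no new patients or data. The downside is that some null results will have to be called inconclusive.

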10. ALTERNATIVES

This is not a treatment study. The alternative is to not participate in this study.

11. DATA AND IMAGE ANALYSIS

11.1 **Image Evaluation and Analysis:** Clip migration will be measured on the post-biopsy mammogram compared to the pre-biopsy mammography exam. Clip migration will be measured by the location of the clip with respect to the biopsy site on the immediate post-clip mammography images. While delayed clip migration has been found in case reports, the number of cases of this phenomenon is not felt to warrant additional mammography exams for this study.⁸ The millimeters of clip migration will be measured on the CC view and on the true lateral (ML or LM) views. Although migration usually only occurs in one plane, both planes will be reviewed and if there is migration in two planes, one component factor (Pythagorean Theorem as has been used on prior studies¹) will be calculated.

11.2 We will consider significant migration is anything greater than 10 mm from the biopsy site. The use of 10 mm has been documented on prior studies and will be considered as a differentiation point in this study between significant and nonsignificant movement. A further reason for the use of the 10 mm cut off is that at this institution, Savi Scout devices are commonly used for localization. This device is 12 mm long and can accurately be placed at a location bridging the biopsy site and biopsy clip. Any complications will be reported.

12. STATISTICAL CONSIDERATION:

This is a single-center prospective randomized study to assess two techniques of clip retraction prior to deployment and to determine which method decreases clip migration better,

retracting the clip deployment apparatus 5 mm before deployment or not retracting. This will help improved accuracy of biopsy site localization and in cases of malignancy, will allow for less complicated, better localized, and improved results of tumor targeting for surgical resection.

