6. PROTOCOL PROCEDURES, METHODS, AND DURATION (LAYMAN'S DESCRIPTION)

After confirmation of patient eligibility, the study coordinator, PI, or participating attending radiologist will obtain written informed consent. The informed consent process may take up to 10 minutes. The patients will be discharged from the study after data has been recorded.

Standard of Care:

The stereotactic biopsy will proceed as normally scheduled. This procedure involves the patient presenting to the fifth floor of The Kirklin Clinic (TKC) at The University of Alabama at Birmingham. Once she checks in, she is escorted to a changing room where she changes into a gown. She is then brought back to the biopsy suite by the technologist. The technologist reviews the biopsy procedure with the patient. The attending radiologist then is notified and joins the technologist and patient in the biopsy suite. The radiologist reviews the biopsy with the patient and obtains informed consent.

Study protocol:

After informed consent for the procedure, the radiologist will discuss the study with the patient after the patient. The patient will have time to ask questions and the radiologist will provide answers. If the patient expresses understanding and agrees to participate in the study, consent will be obtained in written form on a document separate from her biopsy consent document. This will be placed in a secure location and locked in a cabinet in the mammography department on the fifth floor TKC, accessible only to the PI.

Standard of Care:

The procedure will take place as normally planned with the patient being positioned in craniocaudal (CC), lateral-medial (LM), or medial-lateral (ML) position determined by the radiologist ahead of time. The choice of positioning is decided on by the radiologist based on experience and best pathway to obtain to target. Images are obtained to verify the target location. The skin is cleaned and skin/breast anesthetized. A needle (9 gauge 10 cm Eviva vacuum-assisted needle attached to an ATEC vacuum suction machine) is placed to obtain the sample of the biopsy target. The tissue undergoes x-ray imaging to ensure adequate sampling of tissue. Once sampling is considered appropriate, standard steps are performed in the following manner:

1. After biopsy, the cavity is flushed with sterile saline.
2. Tubing is disconnected to allow for suction of fluid from the biopsy cavity. Samples are retrieved from the collection chamber.

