3. ATEC machine is placed on biopsy setting until visualization of x-rayed specimens
4. When samples are determined to be adequately retrieved, the clip will be placed (the same clip will be chosen for all procedures to improve standardization unless the attending radiologist determines another clip would be needed).
5. Biopsy clip is then advanced to the site.

At this point, everything performed will be routine.

Study protocol:

Arm 1: Advancing the clip to the biopsy site and deploying.

Arm 2: Advancing the clip to the biopsy site and retracting 5 mm and then deploying.

Standard protocol

After imaging is obtained to ensure that the clip is visualized, the introducer and clip are removed together.

Patient is then slowly released from mammographic compression maintaining pressure on the breast for at least five minutes. Slow release of pressure is performed.

The patient is then informed of post-biopsy changes. Pressure is held until hemostasis is achieved and a sterile skin glue is applied to the skin incision at the entrance site of the biopsy needle.

A two-view mammogram is performed with the first image obtained in the same position as the biopsy is performed.

Clip migration will be measured on the post-biopsy mammogram compared to the pre-biopsy mammography exam. Clip migration will be measured by the location of the clip with respect to the biopsy site on the immediate post-clip mammography images. While delayed clip migration has been found in case reports, the number of cases of this phenomenon is not felt to warrant additional mammography exams for this study.⁸ The millimeters of clip migration will be measured on the CC view and on the true lateral (ML or LM) views. Although migration usually only occurs in one plane, both planes will be reviewed and if there is migration in two planes, one component factor (Pythagorean Theorem as has been used on prior studies¹) will be calculated.

We will consider significant migration is anything greater than 10 mm from the biopsy site. The use of 10 mm has been documented on prior studies and will be considered as a differentiation point in this study between significant and nonsignificant movement. A further reason for the use of the 10 mm cut off is that at this institution, Savi Scout devices are commonly used for localization. This device is 12 mm long and can accurately be placed at a location bridging the biopsy site and biopsy clip. Any complications will be reported.

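### Combining the full CC-view and lateral-view distances by Pythagoras counts the anterior-posterior axis twice, so some true shifts of 7.07 to 10 mm would be recorded as above 10 mm (minor)

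*Combined protocol and SAP*

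**What the plan says.** Sections 6 and 11.1 give the same measurement rule: "The millimeters of clip migration will be measured on the CC view and on the true lateral (ML or LM) views". The next sentence begins "Although migration usually only occurs in one plane" and continues that "both planes will be reviewed and if there is migration in two planes, one component factor (Pythagorean Theorem" is calculated. The authority for the formula is a citation: "Pythagorean Theorem as has been used on prior studies".

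Neither section says which anatomical axis is read on which view, or whether the value from a view is the full in-view distance or one component. Section 13.2 adds no formula.

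Section 11.2 sets the cut-off: "We will consider significant migration is anything greater than 10 mm from the biopsy site". Section 13.2 uses it for the primary endpoint and its per-arm Clopper-Pearson intervals. The same distance also feeds the per-arm means, the t-test and the secondary models.

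**The concern.** The CC view shows the medial-lateral (ML) and AP axes. The true lateral view shows the superior-inferior (SI) and AP axes. (Here ML means an axis; the protocol also uses it for a projection.) The two in-view distances are therefore not perpendicular legs, because they share AP. The only earlier referent for the two planes is the pair of views just named, so the natural literal reading is to square and add the two in-view distances. A shift purely along AP then appears on both views, triggers the two-plane rule and is recorded too long.

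At stake is whether a patient counted above 10 mm really has a clip more than 10 mm from the biopsy site. Section 11.2 justifies the cut-off partly by a 12 mm localization device that can bridge site and clip, and that argument concerns true distance. The error runs one way: it can raise recorded rates and means but never lower them, and a larger sample does not remove it.

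**Working it through.** **1. The plan's own power figure.** Inputs from section 12.1: 125 per arm, one-sided Fisher's exact test, 5% level. Exact enumeration gives 99.96% for 50 v 20% (Table 1: 99.9%) and 93.5% for 50 v 30% (Table 1: 93.1%). The planned power reproduces and does not depend on this point.

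**2. Geometry (no distributional assumption).**
- True distance: R² = ML² + SI² + AP².
- In-view distances: CC² = ML² + AP²; LAT² = SI² + AP².
- Combined: CC² + LAT² = ML² + SI² + 2·AP² = R² + AP².
- The inflation factor is √(1 + AP²/R²), which runs from 1 (no AP movement) to √2 (pure AP).
- Recorded above 10 mm when AP² > 100 − R². Since AP² ≤ R², this needs R > 10/√2 = 7.07 mm.
- At R = 8 mm, |AP| must exceed √36 = 6.0 mm. At R = 9 mm, it must exceed √19 = 4.4 mm.
- Pure 8 mm AP shift: √(64 + 64) = 11.3 mm. Pure 8 mm ML or SI shift: 8.0 mm, unaffected.

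**3. How often (assumed inputs).** The documents give no component standard deviations (SDs) and no share of clips moving along AP. Assume independent normal components. The needle-axis SD is 10 mm without and 5 mm with retraction. AP and the remaining off-needle axis (SD 5 mm each) each move in a given share of patients. The double count multiplies the AP SD by √2. Rates above 10 mm (no retraction / retraction):

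| Share moving on each off-needle axis | True | Recorded | Extra per 125 | Arm difference, points |
|---|---|---|---|---|
| 10% | 33.6 / 6.4% | 34.5 / 7.6% | about 1 / 1.5 | 27.2 to 26.9 |
| 20% | 35.5 / 8.3% | 37.3 / 10.7% | about 2 / 3 | 27.2 to 26.6 |

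Power in the 20% case goes from 99.99% to 99.96%. Single-axis movement holds in 0.9² = 81% of patients at 10% and in 0.8² = 64% at 20%.

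**4. Bound at the planned rates.** Suppose each clip moves along one axis only and AP movement is the same in both arms. The rise per arm is (AP share) × P(7.07 < |AP| ≤ 10). That probability is 2[Φ(10/s) − Φ(7.07/s)], which is 11.2% at s = 5 mm and at most 16.6% for any s (reached near 8.5 mm).
- AP share 10%: at most 0.10 × 16.6 = 1.7 points, about 2 of 125.
- AP share 20%: at most 0.20 × 16.6 = 3.3 points, about 4 of 125. Then 50/20% becomes at most 53.3/23.3% (power 99.96% to 99.94%), and 50/30% becomes at most 53.3/33.3% (93.5% to 93.2%).

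Mean distance rises by share × (√2 − 1) × s × √(2/π). At 20% this is 0.33 mm for s = 5 mm and 0.56 mm for s = 8.5 mm, equal in both arms.

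**5. Type I error.** The rule is the same in both arms, so if retraction has no effect the recorded rates are equal. The exact size of the one-sided test at equal rates from 20 to 55.5% is 3.7 to 4.4%, below 5%.

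**6. Scale.** The Clopper-Pearson interval for 10/125 (8.0%) is 3.9 to 14.2%, much wider than the shift of about 2 points in step 3.

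**7. Upper illustrations only.** With one third moving on each off-needle axis, 38.0/10.9% becomes 41.0/15.0%, but only (2/3)² = 44% of patients then move on a single axis. With every patient moving on all three axes, 51.6/26.2% becomes 59.8/38.1% and power goes from 99.3% to 96.1%. Neither fits the protocol's statement that movement is usually in one plane.

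**The case against.** Pythagoras combines perpendicular components, so entering two distances that share an axis misapplies the named method. If plane means direction of movement, a pure AP shift is one-plane migration and is recorded correctly. The formula is also adopted from a cited study, which may define its components. All of this stands: the documents leave the definition open and do not prove that any patient would be misclassified. It does not close the gap, because the only values the plan says it will measure are one per view. For an oblique shift, the direction reading avoids the double count only if single-axis components are entered, which is not stated either.

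The protocol's remark that migration is usually in one plane also limits the effect. If plane means view, any AP movement shows on both views, so that remark makes AP movement uncommon. This too stands, and it is why the larger scenarios are set aside.

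A reader might infer that the treatment comparison is biased or its type I error inflated. The documents do not support that. The approaches listed in section 3.2.2 are "Compare different approaches (lateral, medial, superior) to biopsy", so the 5 mm retraction acts along ML or SI, each counted once, and the same rule applies in both arms. A reader might also infer a rise of ten points or so in the recorded rates. That needs nearly every clip to move on several axes, contrary to sections 6 and 11.1.

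**Conclusion.** The point holds, and it is minor. On the literal reading the rule counts AP twice and can place a true shift of 7.07 to 10 mm above the primary cut-off; that part is exact algebra. Its frequency rests on the assumed SDs and AP shares. In the settings closest to the protocol's own description it is about 1 to 3 extra patients per 125 in each arm, with an upper bound of about 4 if 20% of clips move along AP alone. Per-arm rates and mean distances are biased upward by a small amount. The arm comparison, type I error and power are essentially unchanged, provided retraction does not itself alter AP movement. To call this a demonstrated error in the endpoint would go too far, since the direction reading is open and the cited formula cannot be checked.

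**What to change.** In sections 6 and 11.1, record ML from the CC view, SI from the true lateral view, and AP once, as the mean of the two views. Define migration = √(ML² + SI² + AP²) for every patient. This returns the single component when only one axis moves, so the two-plane condition can be deleted. State in section 13.2 that this value is used for the 10 mm cut-off and for all distance analyses.

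The cost is wording in the protocol and SAP, a change to the data form, and one extra caliper reading per view. The two mammographic views are those already taken. Comparability with the cited study may fall slightly if its formula differs. If the intended formula already counts AP once, the change only writes it down.
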